### 6.1. Adverse Events

The verbatim terms used in the CRF by investigators to identify adverse events will be coded using the Medical Dictionary for Regulatory Activities (MedDRA). Any AE starting at or after the initial administration of study agent through the end of the trial is considered as treatment emergent. If the event occurs on the day of the initial administration of study agent, and either event time or time of administration are missing, then the event will be assumed to be treatment emergent. If the event date is recorded as partial or completely missing, then the event will be considered as treatment emergent unless it is known to be prior to the first administration of study agent based on partial onset date or resolution date. All reported treatment-emergent adverse events will be included in the analysis.

The following analyses will be used to assess the safety of participants in the study:

- The incidence and type of AEs.
- The incidence and type of SAEs.
- AEs of severe intensity
- AEs leading to discontinuation of study
- The incidence and type of reasonably related AEs.

These summary tables will provide the count and percentage of participants with 1 or more of the specified AEs by treatment group. In addition to the summary tables, listings will be provided for participants who:

- Had SAEs
- Had AEs leading to discontinuation of study
- Had AEs of severe or life threatening, or fatal based on CTCAE (grade $\geq$ 3) intensity
- Had anaphylactic or serum sickness-like reactions.

Since safety should be assessed relative to exposure and follow-up, most AE summary tables will include average weeks of follow-up and average number of study agent administrations, and injections for each treatment group.

In addition, a participant who had injection site reaction(s) in 30 minutes (+/- 10) post injection at Weeks 0, 1, and 2 were recorded in eCRF. The incidence of injection-site reaction during this time frame will be summarized.

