***Safety Endpoints:***

- Incidence of skin infection treatment-emergent adverse events (TEAEs) requiring systemic treatment from baseline through week 16 and 32.
- Incidence of treatment-emergent serious adverse events (TESAEs) from baseline through week 16 and 32.
- Incidence of TEAEs leading to treatment discontinuation from baseline through week 16 and 32.

\*Each listed time point (in weeks) will be measured separately and treated as an individual endpoint.

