**ADDITIONAL ELEMENTS, WHERE APPLICABLE:**

- Certain protocol-mandated visits to the study site may not be possible during the COVID-19 outbreak. Therefore, temporary measures may be implemented if considered appropriate by the sponsor and investigator to maintain continuity of patient care and study integrity. Certain measures, such as those listed below, may be necessary and should be instituted in accordance with applicable (including local) laws, regulations, guidelines, and procedures:
  - remote (eg, by phone / telemedicine) or in-person, off-site (eg, in-home) interactions between site staff (or designees) and patients for study procedures e.g. those related to safety monitoring / efficacy evaluation / drug product storage and administration (including training where pertinent)
  - procurement of drug product by patients (or designee) or shipment of drug product from the study site directly to patients for at home administration (including the potential for self-administration of drug product)
  - laboratory assessments using a suitably accredited local laboratory; for selected measures (eg, urine pregnancy), home testing may be employed
  - other procedures, eg, imaging, may be conducted at an appropriate facility
- Missed assessments/visits will be captured in the case report form (CRF) for protocol deviations. Discontinuations of drug products and withdrawal from the study should be documented with the prefix “COVID-19-related” in the CRF.
  - other relevant study data elements impacted by the pandemic should also be documented / labeled as “COVID-19-related” in CRFs and / or other study systems, as directed by detailed sponsor guidance. These may include missed / delayed / modified study visits / assessments / dosing, and instances where temporary measures such as those above are implemented.
- The sponsor will evaluate the totality of impact of COVID-19 on collection of key study data and additional data analyses will be outlined in study SAP(s).
- Precaution: for those who may carry a higher risk for severe COVID-19 illness (eg, those aged over 65 years), follow guidance from local health authorities when weighing the potential benefits and risks during participation in the study.

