In the event of an emergency that would require the investigator to be aware of the treatment allocation prior to the end of the trial, the investigator can obtain this information, on a per subject basis, after consultation with the Sponsor's Medical Monitor, if possible. Every effort should be made to consult with the Medical Monitor prior to emergency unblinding. Events that qualify as emergencies are as follows:

- A grade 3 or greater AE which are “probably or definitely” related to study drug, and only if treatment assignment information is essential for the management of the event. This type of reaction would require that the patient receives no further doses and is followed until the resolution of the toxicity.
- Any suspected, unexpected, serious adverse reaction (SUSAR)
- Pregnancy

The investigator may, in an emergency, determine the identity of the intervention through the EDC system. While the responsibility to break the intervention code in emergency situations resides solely with the investigator, it is recommended that the investigator contact the sponsor or its designee if possible, to discuss the particular situation, before breaking the blind. Telephone contact with the sponsor or its designee will be available 24 hours per day, 7 days per week. In the event the blind is broken, the sponsor must be informed as soon as possible. The date and reason for unblinding must be documented in the appropriate section of the eCRF, and in the source document.

Participants who have had their intervention assignment unblinded by the investigator will not be eligible to receive further study intervention but should continue to complete evaluations specified in the Study Calendars (Section 5.2 of the protocol).

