## 4.2. Disposition Information

The number of participants in the following disposition categories will be summarized by treatment group and overall:

- Participants screened: met the inclusion criteria regarding the target indication and signed the informed consent
- Participants randomized
- Participants randomized and received at least 1 study agent
- Participants who completed the study through Week 16 and Week 36
- Participants who discontinued study and the reasons for discontinuation through Week 16 and Week 36

Listings of participants will be provided for the following categories:

- Participants who discontinued study
- Participants who were unblinded during the study period

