## 4.3. Treatment Compliance

Study agent compliance will be summarized descriptively through Week 16 and through the end of the study (Week 36) for the FAS. Number of the participants receiving each scheduled treatment will be summarized. In addition, treatment compliance will also be assessed by protocol deviations related to study agent administration (i.e., incorrect study agent or dose received).

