#### Supplementary Estimands for primary endpoint:

##### Supplementary Estimand 1

Same components as the primary estimand, except for the strategy used for treatment discontinuation.

**Hypothetical strategy:** assess the treatment effect as if the participants would not have discontinued treatment.

Note: Under this hypothetical strategy, EASI data collected after treatment discontinuation will not be used and will be set to missing in analysis.

##### Supplementary Estimand 2

Same components as the primary estimand, except for the strategy used for treatment discontinuation.

**Treatment policy strategy:** assess the treatment effect regardless of treatment discontinuation.

Note: Under the treatment policy strategy, EASI data collected after treatment discontinuation will also be used in analysis.

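### SAP 6.1 plans no output for two of the three protocol safety endpoints: adverse events that stop study drug, and skin infections needing systemic treatment

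*SAP*

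**What the plan says.** The protocol lists its safety endpoints in the synopsis and again in 3.1. One concerns stopping drug: "Incidence of TEAEs leading to treatment discontinuation from baseline through week 16 and 32". Another concerns infection: "Incidence of skin infection treatment-emergent adverse events (TEAEs) requiring systemic treatment from baseline through week 16 and 32". The third is serious TEAEs over the same two periods.

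SAP 6.1 lists the adverse event tables: all AEs, SAEs, AEs of severe intensity, "AEs leading to discontinuation of study", and AEs reasonably related to drug. Listings cover serious events, events leading to study discontinuation, events of grade 3 or above, and anaphylactic or serum sickness-like reactions. Injection-site reactions at Weeks 0, 1 and 2 have their own summary. SAP 6 sets the reporting periods as through Week 16 and through Week 36.

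The neighbouring outputs are:
- Disposition (SAP 4.2): "Participants who discontinued study and the reasons for discontinuation through Week 16 and Week 36".
- Compliance (SAP 4.3): "Number of the participants receiving each scheduled treatment will be summarized".
- Deviations (SAP 4.5): a listing of patients who missed scheduled doses.
- Concomitant medications (SAP 4.6): a summary limited to medications for atopic dermatitis, plus a list of patients given a treatment that could improve it.

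**The concern.** Safety is part of the primary objective (SAP 1.1; protocol 10.5.2). If SAP 6.1 is programmed as written, two of the three named safety endpoints have no result that matches their definition.

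For discontinuation, the SAP counts a different event under a similar name. A patient whose adverse event ends dosing but who keeps attending visits is in the protocol's numerator and not in the SAP's. The error can only run towards fewer drug stops for adverse events.

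For skin infection, the endpoint has two conditions, and the second (systemic treatment) appears in no planned output. Protocol 9.7 names infection and injection-site reactions together as class risks. SAP 6.1 gives the second a dedicated summary and the first none. If the omission is noticed only when results are written up, the list of qualifying terms would be chosen with unblinded data at hand.

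**Working it through.** The documents give no planned figure for either endpoint, so the check is mainly a side-by-side reading.

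**1. Endpoint against output**

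| Protocol 3.1 | SAP 6.1 | Carried over? |
|---|---|---|
| Serious TEAEs, Weeks 16 and 32 | SAE table | Yes, but the later cut is Week 36 |
| TEAEs leading to treatment discontinuation, Weeks 16 and 32 | AEs leading to study discontinuation | No, a different event |
| Skin-infection TEAEs needing systemic treatment, Weeks 16 and 32 | General AE table only | No, the treatment condition is absent |

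The list of analyses in SAP 6.1 is closed. The lists in SAP 2.4 (Week 16 lock), 2.5 (subgroups) and 6.2 (laboratory) each say that they are not exhaustive. SAP 5.2.1 announces and explains its departure from the protocol on multiplicity; SAP 6.1 does neither. This reads as an omission.

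**2. Are stopping drug and leaving the study different events in these documents?** Yes.
- SAP 5.3.2, treatment policy estimand: "EASI data collected after treatment discontinuation will also be used in analysis". That needs patients who are off drug and still assessed. SAP 5.2.2 has the same rule for observed data.
- SAP 1.5.2: patients unblinded by the investigator "will not be eligible to receive further study intervention but should continue to complete evaluations specified in the Study Calendars".
- Protocol COVID-19 Appendix: "Discontinuations of drug products and withdrawal from the study should be documented with the prefix" that marks them as COVID-19-related, so the two are named separately. The same appendix describes stopping drug for a patient at unacceptable risk while continuing follow-up.

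**3. Does another output fill the gap?**
- Reasons for stopping drug: SAP 4.2 gives reasons only for leaving the study. SAP 4.3 and 4.5 show doses received or missed and state no reason.
- Systemic treatment of an infection: SAP 4.6 is limited to atopic dermatitis medications. Protocol 2.9.3 permits systemic anti-infectives, so they would not surface as deviations.
- Severity: grade 3 or greater events and serious events are listed. What has no dedicated display is an event below grade 3 and not serious that stops drug in a patient who stays.

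**4. Size, discontinuation table**
- Patients per arm: 90 / 3 = 30 (protocol 10.1 and 10.2).
- One missed patient: 1/30 = 3.3 points.
- Illustration, with an assumed count because the documents give none: 3 of 30 stop drug for an adverse event (10%). If 1, 2 or 3 of them stay in the study, the SAP table shows 2/30 = 6.7%, 1/30 = 3.3% or 0%. If none stays, it shows 10% and the tables agree.

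**5. Related points in SAP 6, Summaries through Week 36**
- The placebo-to-qw column counts events only from the first bermekimab dose at Week 16: 36 - 16 = 20 weeks, against 36 for qw and q2w.
- Combined Bermekimab is listed but not defined there. With 30 per arm and no dropout it is 60 patients and 60 x 36 = 2,160 patient-weeks without crossover patients, or 90 patients and 2,160 + 30 x 20 = 2,760 with them.
- Protocol 10.3 analyses safety as treated, SAP 6 by randomised group, and the SAP 6 group definitions require both assignment and receipt. These differ only for mis-dosed patients.

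**The case against.** The best defence is that the two discontinuation counts may largely coincide. Protocol 5.3 is headed as discontinuation of therapy but opens with patients discontinued from the study, and sends them to the Early Termination visit. The main protocol text sets out no schedule for staying on study off drug. SAP 1.5.2 covers only emergency unblinding, whose qualifying events are grade 3 or greater AEs, SUSARs and pregnancy; the AEs among these would be listed anyway. Protocol 10.5.2.1 plans neither table, so the gap does not begin with the SAP. Safety is descriptive, with no formal comparison (SAP 6).

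Most of this stands as a limit on size. It does not supply the missing outputs: the endpoint wording is clear, and the SAP's own estimands presuppose patients observed after stopping drug.

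Four stronger readings are tempting, and the documents do not support them.
- A reader might infer that skin infections vanish from the report. They do not; each appears as a term in the general AE table.
- A reader might count each endpoint at each cutoff and report four of six results missing. That counts two omissions twice.
- A reader might infer that drug stops will be understated by a known amount. That depends on how many such patients stay, which is not given.
- A reader might infer that the Week 36 columns mislead on risk. The sentence on comparable follow-up is true for qw versus q2w, and SAP 6.1 puts average follow-up and number of administrations in most AE tables. This discloses the 20 against 36 weeks, though it does not adjust the percentages. Any bias rests on assumed incidences. With constant hazard and 30 per column, an assumed 36-week incidence of 20% becomes 1 - 0.80^(20/36) = 11.7% over 20 weeks, a gap of 8.3 points against a standard error of 9.4. At an assumed 40% the gap is 15.3 against 11.9.

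**Conclusion.** The concern holds as an omission. SAP 6.1 carries over one of three protocol safety endpoints and has no planned output for the other two. For treatment discontinuation, the shortfall is 3.3 points per affected patient in an arm of about 30, and zero if every patient who stops drug for an adverse event also leaves the study. For skin infections, the events are visible but the endpoint cannot be derived from the planned tables. The protocol shares responsibility: 5.3 blurs the two kinds of discontinuation and 10.5.2.1 plans neither table. It also runs the endpoints to Week 32 while defining TEAEs through the last study visit.

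This should be corrected but does not threaten the trial. The primary efficacy analysis is untouched, and the placebo-controlled Week 16 safety comparison has no follow-up imbalance by design. The size rests on equal arms of 30. The Week 36 points are clarifications.

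**What to change.** **Main change**
- SAP 6.1: tabulate and list TEAEs leading to treatment discontinuation. Keep the study-discontinuation table as an extra.
- SAP 4.2: add treatment discontinuation with reasons.
- SAP 6.1: add a table of skin-infection TEAEs requiring systemic treatment, with a MedDRA term list and a stated rule linking an event to a systemic medication. Fix both before the Week 16 unblinding, because that lock includes adverse events (SAP 2.4) and unblinds some sponsor staff (SAP 1.5.2). If that lock has passed, staff who are still blinded should fix them.
- Report both endpoints through Weeks 16 and 32, and state how Week 32 relates to the Week 36 summaries.

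**Clarifications in SAP 6**
- Limit the sentence on comparable follow-up to qw versus q2w.
- State whether Combined Bermekimab includes crossover patients.
- Reconcile protocol 10.3 with SAP 6 on as-treated versus as-randomised.
- Exposure-adjusted rates, or a table of the first 16 weeks on bermekimab, are optional.

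**Cost.** SAP wording and a few tables; sample size and alpha do not change. The treatment-stop date is already needed for the non-responder rule (SAP 5.2.2). The documents do not say whether the AE form records that an event led to stopping drug; if it does not, the CRF reason for drug discontinuation is needed. Medication data may be incomplete after an early stop. The protocol synopsis collects concomitant medications to the end of study, while footnote 5 of the study calendar requires them only to 7 days after the last dose. For patients dosed through Week 31, Day 217 + 7 = Day 224, so both cover Week 32. For early stoppers they differ, and the two passages should be reconciled.

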injector(s) should have no other contact with the participant during the study, should not discuss the participant's treatment with the participant, participant's caregiver, or other site personnel at any time, and will not be permitted to review the participant's medical records, questionnaires, or the electronic CRF prior to each injection. The designated injector(s) should be documented in the source documents at each visit.

Study treatment will be administered weekly in the clinic for 31 weeks with weekly office visits for 32 weeks. Patients will remain at the study site for a minimum of 30 minutes (+/- 10 minutes) after injections at weeks 0, 1, 2, 16, 17 and 18 injections for safety monitoring.

During the 32-week treatment period, patients will attend weekly clinical study visits. Clinical assessments, collection of samples for bermekimab concentrations, and safety testing will be performed at specified clinic visits. After completion of the 36-week study period, data will be locked and analyzed for safety and efficacy endpoints for all arms. In addition to the analyses that will be performed following the formal database lock at the end of the study at Week 36, an additional database lock may be performed at Week 16, and interim analyses utilizing unblinded efficacy data available as the study progresses, may also be conducted to help plan potential future development activities. An internal interim analysis committee (IAC) will be established to review the interim data and formulate recommended decisions/actions. The IAC will consist of at least a clinician and a statistician (neither of whom are involved in study conduct or compound development), one of whom will chair the committee, and may also include other members as required by the nature of the IAs. Details will be provided in a separate IAC charter, which will define the organization and roles and responsibilities of the committee, possible recommendations or requests, and the communication process following IA reviews. Results from the Week 16 database lock and/or interim analyses will not be disseminated to investigators or subjects participating in the study. In addition, results of the interim analyses will not be disseminated to individuals associated with the conduct of the study.

Patients will be monitored at a follow up visit (visit 34/week 36) for safety and clinical assessments after completing the 32 week treatment period.

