## **5. TREATMENT PLAN**

### **5.2 STUDY PROCEDURES**

#### **PLACEBO-CONTROLLED PERIOD**

**Screening (maximum 30 days): The screening period begins once the informed consent is signed.**

- Informed Consent
- Inclusion/ Exclusion
- Demographics
- Medical History
- Concomitant Medications/Treatments
- Physical Exam
- Electrocardiogram
- Vital Signs (blood pressure, pulse, oxygen saturation, respiratory rate and body temperature)
- Height
- Weight
- Body Mass Index (BMI) [BMI= weight (kg)/height (m^2)]
- Patient Diary
- Patient Oriented Eczema Measure (POEM)
- Hospital Anxiety and Depression Scale (HADS)
- Dermatology Life Quality Index (DLQI)
- Investigator's Global Assessment (IGA)
- Eczema Area and Severity Index (EASI)
- Global Individual Signs Score (GISS)
- SCORing Atopic Dermatitis (SCORAD)
- Body Surface Area (BSA) involvement with atopic dermatitis (must be greater than 10%)
- Urinalysis: pH, protein, glucose and blood cells (RBCs and WBCs)
- Blood Draw:

- Chemistry panel: Albumin, Alkaline Phosphatase, ALT, AST, GGT, Bicarbonate (CO2), Calcium, Chloride, Creatinine, Glucose, Potassium, Sodium, Total Bilirubin, Total Protein, Urea Nitrogen
- Hematology Panel: Complete Blood Count (CBC) with differential and platelets
- Infectious disease screening: HIV antibody, Hepatitis C antibody, Hepatitis B panel (HBsAg, anti-HBc, anti-HBs), and interferon gamma release assay (IGRA)
- Serum pregnancy test for WOCBP
- Inflammation Markers: CRP (C-Reactive Protein), ESR (Erythrocyte Sedimentation Rate)
- Randomization to study arm (once confirmed patient has passed screening requirements).

\*\*\*Patients will be monitored at the study site at visits 1, 2, 3, 17, 18 & 19 (weeks 0, 1, 2, 16, 17 & 18) for a minimum of 30-minutes after study drug administration. Vital signs and AE assessments will be done at 30 minutes (+/- 10 minutes) post-injection.\*\*\*

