## 5.2.2 Blinded Active Dosing Period

Study Procedure	Blinded Active Dosing Period																
	V18	V19	V20	V21	V22	V23	V24	V25	V26	V27	V28	V29	V30	V31	V32	V33	
Visit (V)	W17	W18	W19	W20	W21	W22	W23	W24	W25	W26	W27	W28	W29	W30	W31	W32	
Week (W)	D119	D126	D133	D140	D147	D154	D161	D168	D175	D182	D189	D196	D203	D210	D217	D224	
Day (D)	Visit Window (d)																
Treatment: 	±3d																
Administer Study Drug	X	X	X	X	X	X	X	X	X	X	X	X	X	X	X	X	
Con Meds/ Treatments	X	X	X	X	X	X	X	X	X	X	X	X	X	X	X	X	X
Efficacy:																	
Patient Diary (daily)	X	X	X	X	X	X	X	X	X	X	X	X	X	X	X	X	X
IGA, EASI, GISS, SCORAD, BSA				X				X				X				X	
POEM, DLQI, HADS				X				X				X					X
Safety:																	
Physical Examination																	X
Electrocardiogram																	
Vital Signs	X	X	X	X	X	X	X	X	X	X	X	X	X	X	X	X	X
Adverse Events	X	X	X	X	X	X	X	X	X	X	X	X	X	X	X	X	X
Laboratory Testing:																	
Infectious Disease Panel																	
Hematology, Chemistry, Inflammation Markers								X									X
Urinalysis								X									X
Pregnancy Test (WOCBP only)	X	X	X	X	X	X	X	X	X	X	X	X	X	X	X	X	X
PK/PD/ADA:																	
PK/ADA, IL-6, PD, biomarker & research samples (serum/plasma)								X									X

 Patients will be monitored at the study site at visits 1, 2, 3, 17, 18 & 19 (weeks 0, 1, 2, 18, 19 & 20) for a minimum of 30 minutes after study drug administration. Vital signs and AE assessments will be done at 30 minutes (+/- 10 minutes) post-injection.

 Patients will be randomized to treatment arm 1, 2, or 3 and will follow the corresponding treatment plan.

 Assessments/procedures should be conducted in the following order: patient assessments, investigator assessments, safety and laboratory assignments, administration of the study drug.

 Concomitant medications within 30 days before screening until 7 days after the last administration of the study drug must be recorded for the purpose of drug-drug and drug-disease interaction evaluation and signal detection

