## **7. ASSESSMENT OF SAFETY**

Safety will be assessed by monitoring adverse events, vital signs, physical examinations, ECG, and clinical laboratory measurements. Data from ECG will be included in safety analysis only when all of these measures are available for each subject (baseline and last visit). Adverse events will be monitored from visit 1 (post-injection) through visit 34 (week 36). Any serious adverse events whether related to study drug or not will be followed up until resolution.

Study drug, bermekimab, will be administered under close observation in a facility equipped to handle anaphylaxis or injection site reactions. Subjects must be closely monitored at the study site at visits 1, 2 and 3 (for the first three injections) until at least 30 minutes following the administration of the antibody. Vital signs and AE assessments will be done at 30 minutes (+/- 10 minutes) post-injection.

Any grade 3 or greater injection site reaction must be reported to the sponsor within 24 hours of learning of the event.

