### **Summaries through Week 36**

Safety data through Week 36 will be summarized by treatment groups including

1. Placebo → bermekimab qw
2. Bermekimab q2w
3. Bermekimab qw
4. Combined Bermekimab

This allows safety comparisons between each bermekimab regimen through Week 36 based on the similar follow-up time in each group.

The list of actual treatment groups for safety analyses and inclusions of participants and safety events/measurements in each group are defined as follows:

1. **Placebo:** all participants who were randomized to placebo and received treatment with placebo only or received treatment with placebo prior to receiving treatment with bermekimab. For participants who started treatment with placebo but later received bermekimab, the safety events/measurements on and after the first dose of bermekimab will be excluded from this group. Only the safety events/measurements that occurred while the participants had been receiving placebo only will be included in this group.
2. **Placebo → bermekimab 400 mg qw:** all participants who were randomized to placebo started treatment with placebo only and later received treatment with bermekimab qw. Only the safety events/measurements from these participants that occurred on and after their first administration of bermekimab will be included in this group.
3. **Bermekimab 400 mg qw:** all participants who were randomized to bermekimab qw and received bermekimab qw. All the safety events/measurements from these participants that occurred on and after their first administration of bermekimab will be included in this group.
4. **Bermekimab 400 mg q2w:** all participants who were randomized to bermekimab q2w and received bermekimab q2w. All the safety events/measurements from these participants that occurred on and after their first administration of bermekimab will be included in this group.

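### The SAP's timed 30-minute injection-site reaction summary stops at Week 2, so it has no active-drug data from Arm 3, whose first bermekimab visits are Weeks 16 to 18

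*SAP*

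**What the plan says.** SAP 6.1 describes reactions noted about 30 minutes "post injection at Weeks 0, 1, and 2 were recorded in eCRF" and then states: "The incidence of injection-site reaction during this time frame will be summarized". No later weeks are mentioned.

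The protocol gives a longer schedule in two places. The synopsis (Trial Design) keeps patients on site "after injections at weeks 0, 1, 2, 16, 17 and 18 injections for safety monitoring". Section 5.2, Study Procedures, names "visits 1, 2, 3, 17, 18 & 19 (weeks 0, 1, 2, 16, 17 & 18" and adds: "Vital signs and AE assessments will be done at 30 minutes (+/- 10 minutes) post-injection".

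Other protocol passages differ:

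- Section 7 says: "Subjects must be closely monitored at the study site at visits 1, 2 and 3 (for the first three injections".
- Calendar 5.2.1, footnote 2, also stops at visit 3, although that calendar runs to visit 17.
- Calendar 5.2.2, footnote 2, names the six visits but attaches other weeks to the last three: "visits 1, 2, 3, 17, 18 & 19 (weeks 0, 1, 2, 18, 19 & 20".

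Arm 3 receives placebo until Week 15 and first receives bermekimab at visit 17, Week 16 (SAP 1.2; calendar 5.2.1, footnote 7). For the placebo-to-bermekimab safety group, SAP Section 6 states: "Only the safety events/measurements from these participants that occurred on and after their first administration of bermekimab will be included".

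**The concern.** Protocol 9.7 lists injection-site reaction as one of two expected events and links the 30-minute observation to a patient's first three doses. In Arms 1 and 2 bermekimab starts inside the Weeks 0 to 2 window. In Arm 3 that window contains only placebo. Under the SAP's own group definition, the placebo-to-bermekimab group cannot have an observation in a Weeks 0 to 2 table.

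At stake is the precision and completeness of a descriptive tolerability estimate: the rate of early, timed local reactions when bermekimab is started. About a third of the patients who start the drug would not contribute to it.

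**Working it through.** **The documents' own figure.** Protocol 9.7 reports 27 reactions (injection-site or infusion) in 911 patients: 27/911 = 2.96%, which rounds to the stated 3.0%.

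**Coverage of the schedule.**

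| Source | 30-minute visits |
|---|---|
| Protocol synopsis; Protocol 5.2 | Weeks 0, 1, 2, 16, 17, 18 |
| Protocol 5.2.2, footnote 2 | Visits 1–3 and 17–19, the latter labelled weeks 18, 19, 20 |
| Protocol 5.2.1, footnote 2; Protocol 7 | Visits 1–3 |
| SAP 6.1 | Weeks 0, 1, 2 |

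Against the longer schedule, the SAP summarises 3 of 6 assessments. The week labels in calendar 5.2.2 conflict with the calendars themselves, which place visit 17 at Week 16 and visit 18 at Week 17.

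**Patients with active-drug data.** About 90 patients are randomised 1:1:1, so about 30 per arm.

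- In the SAP summary: Arms 1 and 2, 30 + 30 = 60.
- With Weeks 16–18 added: 60 + 30 = 90 if every Arm 3 patient crosses over. The share now absent is 30/90 = 33%.
- If only 24 to 27 cross over (assumed range): 24/84 = 29% to 27/87 = 31%.

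These are patients, not injections. Arm 2 alternates bermekimab with placebo, so one of its Week 1 and Week 2 injections is placebo.

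**Upper 95% limit on the rate if no reaction is seen.** One-sided: 1 − 0.05^(1/n). Two-sided exact: 1 − 0.025^(1/n).

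| n | One-sided | Two-sided |
|---|---|---|
| 60 | 4.9% | 6.0% |
| 90 | 3.3% | 4.0% |
| 30 (Arm 3 alone) | 9.5% | 11.6% |

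With 24 to 27 crossing over, the one-sided limit is 1 − 0.05^(1/84) = 3.5% to 1 − 0.05^(1/87) = 3.4%.

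**Chance of seeing at least one reaction.** 1 − (1 − p)^n with p = 27/911 gives 83.6% for n = 60 and 93.3% for n = 90 (59.4% for Arm 3 alone). Applying that rate to the 30-minute window is an assumption, because it covers other indications and includes intravenous dosing. The range is:

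| Assumed p | n = 60 | n = 90 |
|---|---|---|
| 1% | 45.3% | 59.5% |
| 5% | 95.4% | 99.0% |
| 10% | 99.8% | about 100% |

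**The case against.** A reader might infer that Arm 3's reactions at first exposure drop out of the safety analysis. The documents do not support that. SAP 6.1 includes every reported treatment-emergent event, and SAP Section 6 gives placebo-to-bermekimab its own column through Week 36. A Week 16 reaction reported as an AE is therefore tabulated. Post-injection vital signs are summarised under SAP 6.3. Only the timed 30-minute incidence is missing.

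Nor is SAP 6.1 the only place where injection-site reactions are analysed. SAP 7.2.2 offers a summary by antibody status. It is conditional on enough antibody-positive patients and is not timed, so it does not fill this gap.

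A reader might also take the six-visit schedule as settled and the SAP as simply departing from it. But the SAP's three weeks match Protocol 7 and calendar 5.2.1, so part of the problem lies in the protocol. The SAP's past-tense reference to the eCRF also suggests that a timed field may exist only for Weeks 0 to 2. In that case a new table alone would not be enough.

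Finally, injection-site reaction is not among the listed safety endpoints, safety is descriptive throughout, and the Week 16 to 18 data have no concurrent placebo arm. All of this stands and keeps the severity low. It does not remove the gap: the synopsis and Section 5.2 schedule the assessment, and the SAP does not say what will be done with it.

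**Conclusion.** The point holds in a limited form. As written, the timed summary has active-drug data from about 60 of up to about 90 exposed patients and none from Arm 3. The zero-event one-sided 95% limit is 4.9% instead of 3.3% (two-sided, about 6.0% instead of 4.0%). The figures for 90 assume about 30 patients per arm and full crossover in Arm 3, so they are the most that could be gained. Whether timed data exist at visits 17 to 19 cannot be told from the documents. Severity is low: the primary endpoint, power and alpha are untouched.

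**What to change.** - **SAP 6.1:** extend the descriptive 30-minute summary to Weeks 16, 17 and 18, showing placebo-to-bermekimab beside the two continuing arms. Keep it separate from the randomised Weeks 0 to 2 comparison and do not pool the two periods.
- **Data source:** confirm what the eCRF captures at visits 17 to 19. If there is no timed field, derive the events from AE onset date and time where recorded, and state the limitation in the SAP and the report.
- **Protocol:** reconcile the synopsis and Section 5.2 with Section 7 and calendar 5.2.1, footnote 2 (visits 1 to 3 only), and with calendar 5.2.2, footnote 2 (week labels for visits 17 to 19).

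The cost is one extra descriptive table, plus some derivation work if no timed field exists. Its Week 16 to 18 rows must be read without a concurrent placebo arm.
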